
Exclusion Criteria:
	
 • Suspected or known to be sensitive or allergic to midge bites; • Participated in an interventional study (other than a biting insect challenge study) in the previous 3 months; • Participated in a biting insect challenge study in the previous 72 hours; • Aware of having any cardiovascular or respiratory disorder (whether active or inactive) (e.g. asthma); • Individuals with localized skin disorders affecting the forearm; • Allergic to any of the test product ingredients; • Extensive tattooing or other conditions of the forearm which would make interpretation of the bite test results difficult; • Women who are pregnant, nursing or intending to become pregnant; • Previous anaphylaxis; • Aware of having a compromised immune system;(an immune system that is temporarily or permanently incapable of working at full capacity); • Phobia of flying insects; • Travelled to a mosquito-borne disease endemic area in the last 3 months.

Efficacy Endpoint(s):
	
Primary: Median Complete Protection Time for the repellent products, tested against Culicoides nubeculosus midges.
 
Secondary: Percentage protective efficacy of the repellent products, tested against Culicoides nubeculosus midges.

Safety Endpoint(s):
	
Adverse event data will be collected and summarised.

Statistical Methods:
	
Median Complete Protection Time will be calculated using the Kaplan Meier survival-function.
 
Two-way analysis of variance followed by Tukey's tests or general linear mode will be used to compare the mean complete-protection time for the tested repellents

Investigation Site(s):
	
Single-centre: Arthropod Control Product Test Centre (arctec), Chariot Innovations Limited, a wholly-owned subsidiary of the London School of Hygiene & Tropical Medicine (LSHTM).

TABLE OF CONTENTS

1. INTRODUCTION.....	7
2. OBJECTIVES.....	7
3. STUDY DESIGN	7
3.1. STUDY ENDPOINTS.....	8
3.2. RISKS AND BENEFITS	8
3.2.1. Midges	8
3.2.2. Product	8
4. PARTICIPANT ENTRY	9
4.1. SCREENING PROCEDURES	9
4.2. INCLUSION CRITERIA	9
4.3. EXCLUSION CRITERIA	10
4.4. WITHDRAWAL CRITERIA.....	10
5. RANDOMISATION AND ENROLMENT	11
6. TREATMENTS	11
7. SAFETY REPORTING FOR NON-DRUG TRIALS.....	12
7.1. DEFINITIONS	12
7.2. REPORTING PROCEDURES	12
7.2.1. Non serious AEs	12
7.2.2. Serious AEs	12
8. TEST METHODOLOGY.....	13

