- Rinse with clean water if the eyes come into contact with the repellent, and seek medical advice from a first-aider (dial 0 to ask reception or look up 'First aid' in the LSHTM Telephone Book)
- There will be a minimum of 72 hours between product tests in order to minimise any possibility for sensitization to products over time.
- Report any adverse events

There is no evidence to suggest that the active ingredients present any risk to pregnant or lactating women or the unborn child. However, since participants will be exposed to and may experience increased sensitivity to midge bites, pregnant women will not be included in the study.

General risks to participants associated with involvement in this study will be addressed by adhering to ICH GCP², the Declaration of Helsinki³, the Data Protection Act⁴ and all applicable regulatory requirements.

There will be no benefit to participants. The results of this study will inform the products labelling.

4. Participant Entry

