4.4. Withdrawal Criteria

Participants can stop at any time without giving a reason for withdrawing. Data collected to the point of withdrawal will be used in the analysis of the study, unless the participant requests that their data is not used, in which case it will be removed from the database. Participants may also be removed at the discretion of the Chief Investigator, where continued participation may affect the safety of the participant or where there is a development of any condition which might interfere with study participation.

5. Randomisation and Enrolment

Volunteers will be recruited through standard recruitment methods, including emails, posters, leaflets and other advertising routes to staff and students of LSHTM and other members of the public. Volunteers will be fully informed before the study and it will be made clear that they can withdraw from the study at any time. Volunteers will be given and asked to read the Participant Information Sheet and Product Information Sheet which describes the tests which they will take part in, and a consent form which must be signed before the test begins.

6. Treatments

NEO-INNOVA HEALTHCARE LIMITED will provide two products to be tested containing 35% and 40% PMD, and one positive control containing 20% Picaridin. The positive control product is currently marketed as a midge repellent, while PMD is a recommended active ingredient, which has been evaluated for safe use by the U.S. Environmental Protection Agency (USEPA)¹. Therefore, humans have already used the products. The products will be applied at a rate of 1.67 $\mu\text{l}/\text{cm}^2$. The products will be applied to the measured forearm of each participant. This dose does not exceed the maximum daily limit for PMD or Picaridin.

7. Safety Reporting for Non-Drug Trials

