8.4. Protective Efficacy

In order to determine Protective Efficacy over time, the tests will continue every hour as described in section 8.3 until at least 50% of midges are probing or biting compared with control (i.e. 50% Protective Efficacy), or until 12 hours post application.

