9.2. Data analysis

The endpoint for Complete Protection Time will be time to treatment failure for each participant test. Treatment failure is the time at which the product no longer provides complete protection, which is determined as the time at which one probe or bite occurs in a 1 minute test, followed by a confirmatory probe or bite within 30 minutes. Using IBM SPSS Statistics 20, the times to treatment failure will be analysed using Kaplan-Meier Survival functions, and from these the median Complete Protection time and 95% confidence intervals will be calculated.

A linear regression will be used to compare the mean complete-protection time for the tested repellents. As a sensitivity analysis we will use linear regression to estimate the mean CPT difference between groups, but we will generate robust standard errors by relaxing the assumption of independence of observations between the same participant within the study, allowing for correlation between observations from the same participant in the variance-covariance matrix.

The Protective Efficacy over time from application will be calculated using the formula below at each hour and presented as a summary table and graph. Using IBM SPSS Statistics 20, the PE will be analysed using a two-way analysis of variance followed by Tukey's tests or generalised linear model.

$$PE = \frac{\text{Midges probing on control} - \text{Midges probing on treatment}}{\text{Midges probing on control}} \times 100$$

Adverse Events will be tabulated and included in the study report. Adverse events occurring after the end of participant participation but before the end of the study will be listed separately.

10. Safety and Data Monitoring

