10.2. Adverse events

Volunteers will be monitored throughout the duration of the tests by investigational staff for any adverse events. If any adverse events related to insect bites or the repellent products are apparent at any time during the trial, testing will stop immediately and details of how to access treatment will be offered. Volunteers can only participate in a test a minimum of 72 hours after the screening bite test and participants with known allergies to any of the product ingredients will not be eligible to take part.

Within 72 hours after laboratory testing an email will be sent to participants asking them to report any adverse events that might have occurred since the end of testing.

Adverse events that occur >72 hours after the end of participation in the trial will be passively monitored.

An adverse event which is ongoing at the time of participant withdrawal or completion will be followed up until it resolves or until 30 days after the participant terminates from the study, whichever comes first.

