Appendix 3: Flowchart for Safety Reporting

Appendix 4: Sample Size Calculation for a comparison trial between a positive control and two midge repellent products

A sample size calculation was done using CPT data from a previous study of a repellent against *Culicoides nubeculosus*. The sample size was calculated using the sample size formula for the comparison of 2 means with equal standard deviation. The required sample size per group is given by:

$$n = \frac{2\sigma^2}{\delta^2} f(\alpha, \beta)$$

Where δ^2 is the difference between the mean CPTs of 2 treatment groups, σ is the standard deviation of both treatment groups for one comparison which are assumed to be equal. $f(\alpha, \beta) = (z_{1-\alpha/2} + z_{1-\beta})^2$, which varied depending on the specified values of α and β .

Sample size calculation outcomes

The analysis revealed that for an experiment to compare mean CPT (in min) between any PMD products with Picaridin 20%, assuming a difference in mean CPT of 120 min, with a power of 80% and a significance level of 5%, 7 participants would be required.

A Bonferroni correction was applied for this analysis. The significance level at 5% ($\alpha = 0.05$) was divided by the number of comparisons being made to maintain overall significance level (here divided by 2, as 2 concentrations of PMD are being compared to Picaridin 20%).

Sample size calculation outcomes (with Bonferroni correction) when comparing between two PMD midge repellents and a Picaridin positive control.

Assumption of difference in mean CPT between any PMD group with Picaridin group (minutes)	Number of participants required per arm		
	Alpha = 5% Power = 70%	Alpha = 5% Power = 80%	Alpha = 5% Power = 90%
60	21	26	33
80	12	15	19
100	8	10	12
120	6	7	9
180	3	3	4

If only two arms are compared a Bonferroni correction would not be necessary and the numbers of participants needed for the study are slightly smaller.

Sample size calculation outcomes with the assumption of difference in mean CPT between one midge repellent and a Picaridin positive control.

Assumption of difference in mean CPT between PMD and Picaridin group (minutes)	Number of participants required per arm		
	Alpha = 5% Power = 70%	Alpha = 5% Power = 80%	Alpha = 5% Power = 90%
60	17	21	28
80	10	12	16
100	6	8	10
120	5	6	7
180	2	3	4

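### Section 9.2 compares mean CPT by linear regression with no rule for sessions that end before treatment failure; an early stop entered as a failure distorts the PMD-versus-Picaridin difference

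*Combined protocol and SAP*

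**What the plan says.** Section 9.2 defines CPT as the time to treatment failure in each participant's test, where failure is a probe or bite followed by a confirmatory one. For the medians, "the times to treatment failure will be analysed using Kaplan-Meier Survival functions". For the comparison of products, "A linear regression will be used to compare the mean complete-protection time for the tested repellents". The sensitivity analysis is a second linear regression that changes only the standard errors, to allow for correlation within participant. The synopsis (Statistical Methods) names other methods for the same comparison: "Two-way analysis of variance followed by Tukey's tests or general linear mode will be used to compare the mean complete-protection time".

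Three provisions can end a session before failure:

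- Section 10.2: "If any adverse events related to insect bites or the repellent products are apparent at any time during the trial, testing will stop immediately".
- Section 4.4: participants may withdraw at any time, and "Data collected to the point of withdrawal will be used in the analysis of the study".
- Section 8.4: testing runs to 50% protective efficacy "or until 12 hours post application".

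No section says whether such a session is censored, counted as failed, set to 720 min or left out. Section 4.4 keeps the data of a participant who withdraws but does not say how they enter a mean CPT. It does not cover the other two routes.

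Appendix 4 sizes the study on the difference in mean CPT, "assuming a difference in mean CPT of 120 min, with a power of 80"%, and Section 3.2.2 states the use: "The results of this study will inform the products labelling".

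**The concern.** For an unfinished session the CPT is known only to exceed the last test completed. Kaplan-Meier can carry such a time. Linear regression, ANOVA and the general linear model cannot: the analyst must either enter the stop or limit time as the CPT or drop the session. The plan does not choose, and its sensitivity analysis would not reveal the effect. Section 3 states that there is no blinding, so the choice could be made with the product results in view.

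Comparison is part of the primary objective, and the difference in means is what the seven volunteers were chosen to detect. With seven sessions per product, one early stop matters. Take mean CPTs of 540 and 420 min. If one longer-acting session stops at 120 min and that time is entered, the difference is (6 × 540 + 120)/7 − 420 = 480 − 420 = 60 min instead of 120.

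**Working it through.** **1. The plan's own figure.** Appendix 4 uses n = (2σ²/δ²)(z₁₋α/₂ + z₁₋β)², with α = 0.05/2 = 0.025 after Bonferroni and δ = 120 min. The SD is not given. Solving back from the tables, σ = 68.9 min with rounding up reproduces all 30 cells. For the chosen design, 2 × 68.9²/120² × (2.241 + 0.842)² = 0.659 × 9.505 = 6.27, so 7. Because the SD was fitted, this shows that the tables are consistent. It does not confirm the SD.

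**2. Assumptions.** The documents give no mean CPT and no stop rate, so both are assumed. CPT is normal with SD 68.9 min and rounded up to the next hourly test. The limit is 12 h. Seven volunteers test three products, the third midway between the other two. The true difference is 120 min, one contrast is tested at 0.025, and stops are independent between sessions.

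**3. Early stops, by hand.** Let p be the chance of a stop at each hourly insertion. A session that would fail at hour T then has mean recorded time [1 − (1 − p)^T]/p hours. True means of 6 and 8 h become about 6.5 and 8.5 h on the hourly grid. With p = 0.02:

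- shorter-acting: (1 − 0.98^6.5)/0.02 = 6.153 h = 369.2 min; sessions stopped 7 × (1 − 0.98^6.5) = 0.9
- longer-acting: (1 − 0.98^8.5)/0.02 = 7.889 h = 473.4 min; sessions stopped 7 × (1 − 0.98^8.5) = 1.1
- difference: 473.4 − 369.2 = 104.2 min

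**4. Early stops, simulated (40,000 trials, 6 v 8 h, linear regression).**

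| Stop chance per insertion, all products | Stopped of 7 (short/long) | Stop time entered: difference, power | Stopped sessions left out: difference, power |
|---|---|---|---|
| none | 0/0 | 120 min, 76% | 120 min, 76% |
| 2% | 0.9/1.1 | 104 min, about 35% | 120 min, 66% |
| 5% | 2.0/2.5 | 84 min, 15% | 120 min, 51% |
| 10% | 3.5/4.1 | 59 min, 6% | 120 min, 28% |

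Power falls faster than the estimate because a few very short recorded times inflate the residual variance. If stop chances differ by product, the error can go either way: 54 min with 2% on the shorter- and 5% on the longer-acting product, 134 min with these reversed. Leaving stopped sessions out gives 117 and 122 min in these two cases.

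**5. The 12-hour limit, no early stops.**

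| True means | 720 min entered: difference, power | 12-hour sessions left out: difference |
|---|---|---|
| 8 v 10 h | 117 min, 76% | 114 min |
| 9 v 11 h | 106 min, 74% | 96 min |
| 10 v 12 h | 79 min, 65% | 68 min |
| 11 v 13 h | 41 min, 38% | 41 min |

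The middle column estimates the difference in mean protection time restricted to 12 h. It falls below 120 min because it is a different quantity, not because of a coding error.

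**6. A regression for right-censored times.** With a normal model, estimates were about 117 min at 2% shared stops (power about 75%), 121 at 5%, 120 and 117 for the two unequal cases, and 116 at 9 v 11 h. It was less good at 10% stops (mean 129) and at 10 v 12 h (111, and 105 in a second run). Null rejection was about 4 to 5% at a nominal 2.5%, so part of the 75% is inflation. A participant-clustered test on 6 degrees of freedom had about 60% power with no stops and 56% at 2%, and rejected 4.3% of null trials at 5% stops.

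**The case against.** The strongest reply is that the primary endpoint, the Kaplan-Meier median, is unharmed, that naming Kaplan-Meier already implies censoring, and that the missing item is one sentence. For the medians this stands.

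It also stands that linear regression can deal with the 12-hour limit. If 720 min is entered, the target is the restricted mean difference, and power hardly moves until the longer-acting product averages about 12 h. A reader might infer that the limit alone invalidates the comparison. Nothing in the documents places CPTs in that range.

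The 5% and 10% stop rates have no basis in the documents. They would stop about 6 to 7 and about 11 of 21 sessions. Volunteers pass a bite test (4.1), are chosen for insensitivity to bites (4.2), and the study is rated low-risk (10.1). A reader might infer from the 59 min row that the planned comparison will fail; the documents do not support that. They do not rule out the 2% case either. Section 10.2 sets no severity threshold, Section 7.2.1 counts local redness and swelling as an adverse reaction, and the untreated arm enters the cage every hour (8.3).

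Finally, a censored regression with seven participants is approximate and somewhat anti-conservative. That is a reason to report linear regression beside it under a stated coding rule. It does not excuse having no rule. The restricted-mean argument does not rescue an early stop, because a stop at 2 h is not a protection time of 2 h.

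**Conclusion.** The concern holds for the comparison of products, and mainly for early stops. The plan allows sessions to end before failure but compares CPT only by methods that take every time as observed, and its sensitivity analysis does not address this. That is a mismatch of method as well as a missing detail.

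With about 1 of 7 sessions per product stopped and the stop time entered, a 120 min difference is estimated as about 104 min and power falls from about 76% to about 35%. This rests on an assumed 2% stop chance per insertion, assumed means of 6 and 8 h, and an SD inferred from Appendix 4. If no session stops early and mean CPTs are well below 10 to 11 h, the bias is negligible.

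The documents do not support reading this as a fault in the Kaplan-Meier medians, which are sound once unfinished sessions are censored. Nor do they show that label claims would be wrong: Section 3.2.2 does not tie the labelling to the difference in means. The change should be made before data are seen; confidence in the size of the effect is medium.

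**What to change.** Add to Section 9.2:

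> A session ending before treatment failure is right-censored at the last completed treated-arm test in the Kaplan-Meier analysis and in the comparison of products. If any session is censored, products are compared with a regression for right-censored times that accounts for participant; if none is, the planned linear regression is used. Linear regression is also reported, with 12-hour sessions entered as 720 min (difference in mean CPT restricted to 12 h) and sessions stopped early left out. Stopped sessions are listed by product and reason.

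Align the synopsis with this text and leave the Section 10.2 safety stop unchanged.

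The cost is one paragraph and one synopsis line, with no extra visits, participants or data: the case report form already records test times and adverse events (10.3). With no censored session the two regressions give the same estimate. The downside is small-sample inference, so p-values from the censored model should be labelled approximate. The software named in 9.2 must be checked for a suitable model.

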7.2.1. Non serious AEs

All adverse events should be recorded on the Adverse Event Record Form (Appendix 1) and Adverse Event Monitoring Questionnaire (Appendix 2) and entered into a spreadsheet and stored on the "I" drive with access limited to the *arctec* study staff. All adverse events will be reported to NEO-INNOVA HEALTHCARE LIMITED. Depending on the nature of the event the reporting procedures below should be followed, see Appendix 3 for a flowchart of safety reporting.

In the event of minor adverse reactions such as localised skin redness and swelling, volunteers will be directed to contact the nearby GP surgery at [name] ([contact]) or their own GP.

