8.3. Complete Protection Time

The repellent product will be applied to the right arm of the participant. A combined fitness check and control test is conducted as described in section 8.1. Immediately after, the right (treated) arm is inserted into the cage for 1 minute. The number of midges probing or biting the arm after 1 minute will be counted and recorded. A further hour post-application of the repellent product, the left arm (control) of the volunteer is again inserted into the cage. The number of midges probing or biting the arm after 1 minute will be counted and recorded and the arm removed from the cage. If less than 10 midges land on the untreated arm during this 1 minute test the cage will be refreshed with new midges and the test repeated. Immediately after, the right (treated) arm is again inserted into the cage for 1 minute. The number of midges probing or biting the arm after 1 minute will be counted and recorded. This procedure will be repeated at hourly intervals throughout the test.

If at any stage, more than one midge probes or bites on the treated arm in the 1 minute test, this represents the end of the testing for Complete Protection Time. If, at any stage, one midge probes or bites on the treated arm in the 1 minute test the test will be repeated half an hour later. If there is a confirmatory probe or bite during the test, this represents the end of the testing for Complete Protection Time but testing for Protective Efficacy (as described in section 8.4) will continue at hourly intervals, with the next test taking place 30 minutes later. If there is no confirmatory probe or bite during this test, testing will resume, with the next test to take place 30 minutes later. All testing for Complete Protection Time and Protective Efficacy must be conducted at hourly intervals.

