Appendix 1: Adverse Event Record Form

Study Title:

Volunteer number	reference	Date	Side effect/adverse event	Related to the product	Comments	Action taken
				Y/N/ don't know		

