Appendix 2: Adverse Event Monitoring Questionnaire

[figure not shown]
To be completed by person who experienced the Adverse Event	
Name (first name SURNAME)	
Date of birth dd/mm/yyyy	
Phone number	
Mobile number	
E-mail address	
What kind of adverse event did you experience? e.g. skin rash, burning sensation, severe allergic reaction	
How long did the adverse event last?	
How serious was the event? mild / moderate / severe / life threatening	
Did you take any action to resolve the event?	
Was any treatment required?	
Did you visit A&E? Please enter details	
Did you stay in hospital overnight? Please enter details (no. nights/admission)	
Outcome unresolved / resolved / resolved with sequel	
To be completed by arctec trial manager	
Participant ID	
Study title	

Study code	
Type of study e.g. repellent, impregnated clothing, after-bite cream	
Exposure type e.g. chemical, mosquito bites, bed bug bites	
Exposure area e.g. forearm, legs	
Active ingredient	
Report date dd/mm/yyyy	
Other event Please enter details	
Likelihood of Adverse Event being related to study unrelated / unlikely / possible / probably / definite	
Serious Adverse Events	
Was the event serious? yes / no	
Admitted to Intensive Care Unit? yes / no	
Seriousness criteria (please tick)	
life threatening	
required hospitalisation	
prolonged hospitalisation	
congenital anomaly	

disabling/incapacitating	
important medical event	
required intervention to prevent impairment or damage	
Fatal	
If fatal, date of death dd/mm/yyyy	
Primary cause of death	
Was a post-mortem performed? yes / no	
Date adverse event become serious dd/mm/yyyy	
Possible contributing factors to SAE other than study participation or underlying disease being studied Please give details	
None apparent	
Concurrent illness, disease or other external factors	
Concurrent medication	
Study procedure	
Accident, trauma, or other external factors	
Other	
Relevant concomitant medication at time of SAE yes / no – if yes please provide details	
Treatments/procedures for SAE yes / no – if yes please provide details	

Relevant medical history (include only relevant past or concurrent medical disorder, surgeries, etc that might help explain the SAE)
 
yes / no – if yes please provide details
	

Relevant laboratory testing
 
yes / no – if yes please provide details
	

If relationship to study participation was unrelated, provide causality
 
Please give specific details
	
Discontinuation of study participation	

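### The adverse event forms have no field for the side of a local reaction, the PMD strength or the onset time, and Section 9.2 plans no tabulation by product or arm

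*Combined protocol and SAP*

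**What the plan says.** The synopsis gives the safety endpoint as "Adverse event data will be collected and summarised". Section 9.2 adds "Adverse Events will be tabulated and included in the study report", with events after a participant's last involvement listed separately. Neither place mentions product, arm or cause.

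Section 7.2.1 requires both Appendix 1 and Appendix 2 for every adverse event. Appendix 1 holds the volunteer reference, a date, the event, "Related to the product" (yes, no or don't know), comments and action taken. In Appendix 2 the trial manager completes "Exposure type e.g. chemical, mosquito bites, bed bug bites", "Exposure area e.g. forearm, legs", "Active ingredient", a report date, and a rating of how likely it is that the event is related to the study.

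On layout, Section 8.3 states: "The repellent product will be applied to the right arm of the participant". Sections 8.1 and 8.3 use the left arm as the bare control at every test. Section 3 says that there is no blinding. Section 8.5 sets the aim of the follow-up: to assess reactions to the bites, the products, or both.

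**The concern.** In each session a participant has product on one forearm and none on the other, and both forearms go into the cage. Section 3.2.1 expects that bites may cause irritation and itching. A red or itchy forearm reported afterwards could come from the midges, the product, or both. The most useful plain fact for telling these apart is which arm reacted, and neither form asks for it.

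At stake is the usefulness of the safety summary. If local reactions are reported, a table without product or arm will not show whether they gather on treated skin or follow one PMD strength. A side that is not noted at the time may be lost for good.

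**Working it through.** The plan gives no figure to reproduce. The check compares what the two forms ask for with what Section 10.3 lists for the case report form (CRF).

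| Fact | Appendix 1 | Appendix 2 | CRF list, Section 10.3 |
|---|---|---|---|
| Active ingredient | no | yes | through product details |
| PMD strength, 35% or 40% | no | no | through product details |
| Onset date and time | a date, not defined as onset | report date, duration, and date the event became serious | visit date and application details; onset not listed |
| Side of reaction | no | no; area of exposure only | not listed |
| Product or bite as cause | judgement | judgement | not listed |

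**Product.** The field "Active ingredient" separates PMD from Picaridin but not 35% from 40% PMD. Section 10.3 puts participant number and visit date on every CRF page and lists product details for each test visit. If those details identify the formulation, participant and date normally give the product.

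**Where that linkage can fail.** Product tests may be as little as 72 hours apart (Section 3.2.1), and follow-up takes place within 72 hours of a test (Section 8.5). A reaction first noticed or reported after the next visit could be dated to that visit and so to the wrong product. The date in Appendix 1 is not defined as onset. A report date with a duration, as in Appendix 2, gives onset only if it is known when the event ended.

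**Side.** "Exposure area e.g. forearm, legs" asks where exposure took place, not where the reaction appeared, and does not ask for left or right. Both forearms are exposed, so the answer forearm does not settle the side. Linkage to the CRF does not help, because product and session are the same whichever arm reacted. Section 10.2 has post-test events sought by email, so staff may never see the arm.

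**Cause.** Two fields address cause: "Related to the product" and "Exposure type e.g. chemical, mosquito bites, bed bug bites". Both are opinions given with the product known. A session can involve both chemical and bites. The rating of relation to the study does not separate them either, because both are study exposures.

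**What recording the side would give.** There are 7 participants and 3 products, so 7 × 3 = 21 sessions, 7 per product, each with one treated and one untreated arm. If no session with a given product showed a reaction on the treated arm only, the one-sided 95% upper bound on that rate would be

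1 − 0.05^(1/7) = 1 − 0.652 = 0.348, or about 35%.

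That is enough to describe a pattern, but not to exclude local intolerance.

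**The case against.** The strongest reply is that little is truly missing. Appendix 2 names the active ingredient, the CRF supplies the strength, and two fields record attribution. A reader might infer that the plan cannot tell the products apart or cannot separate product from bite reactions at all. The documents do not support that: the first is usually possible by linkage, and the second is done by judgement. What remains is that the linkage is not stated, late events can be misassigned, and the judgement has no recorded side to rest on.

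It can also be said that open entries (the event description, comments, exposure area) allow someone to write right forearm, and that the CRF's own adverse event pages are not reproduced. Both are fair. But an entry that nobody is prompted to make will be made unevenly, and the Section 10.3 list does not mention side.

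A third reply is that the untreated arm is a poor control. This stands in part. The bare arm goes in every hour and needs at least 10 landings for the cage to count, while the treated arm should receive few bites until the product fails. A reader might infer a clean within-person comparison; the design does not give one. The imbalance still makes one pattern informative: a reaction only on the arm that is expected to be bitten less points towards the product. Reactions on both arms stay ambiguous.

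Two further inferences should be avoided. Section 3.2.2 says that eye irritation from the finished product is unstudied; it does not say that about skin tolerance. And the documents give no rate of bite reactions. Volunteers are screened for low sensitivity (Sections 4.1 and 4.2), so one should not assume that bite reactions will swamp the table.

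Finally, adverse events are a descriptive endpoint in a study classed as low-risk (Section 10.1), and a plan to tabulate does not rule out a table by product. This limits the weight of the point but does not answer it.

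**Conclusion.** The point holds as a gap in data capture and table layout. Neither form has a field for side of reaction, PMD strength, or onset date and time, and Section 9.2 plans no tabulation by product or arm. Product is usually recoverable; side is not, except by chance. Attribution therefore rests on unblinded opinion, although the fixed right-treated, left-bare layout offers a more objective aid.

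The effect is confined to the safety summary; protection time and protective efficacy are untouched. With 7 sessions per product, the better table would still be descriptive, as the 35% bound shows. The conclusion assumes that the CRF's adverse event pages, which are not reproduced, do not already ask for side and onset, and that its product details identify the formulation. It does not depend on any assumed frequency of bite reactions. The change is worth making because it is cheap, and because the side must be noted at the time or it may be lost.

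**What to change.** 1. Add three items to Appendices 1 and 2: product code (35% PMD, 40% PMD or Picaridin); side of the reaction (right treated, left untreated, or both); and onset date with time after application. Ask for side and onset in the follow-up email as well.
2. State in Section 9.2 or 10.3 that each event is linked to its session by participant number and visit date, and how an event that begins or is noticed after a later session is assigned.
3. In Section 9.2, tabulate local events by product and, within product, as treated arm only, untreated arm only, and both arms.
4. State the limits with the table: the untreated arm is expected to receive more bites, both-arm reactions are ambiguous, and with 7 participants per product the table is descriptive.

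The cost is a few form fields, one sentence on linkage and one table, with no extra visit, staff or procedure.
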